#### 9.4.1 Secondary Analyses

For evaluation of the secondary efficacy comparisons, 95% confidence intervals will be provided for the treatment differences of i) DHA-PQP plus TQ versus DHA-PQP plus PQ and ii) DHA-PQP plus PQ versus DHA-PQP alone. An exploratory p-value will also be provided for the DHA-PQP plus PQ versus DHA-PQP alone comparison.

A secondary per protocol analysis will also be performed, excluding subjects who deviate significantly from the protocol. If a subject misses a scheduled study visit from day 28 onwards, they will automatically be excluded from the per protocol population.

Statistical comparisons (i) DHA-PQP plus TQ versus DHA-PQP alone, ii) DHA-PQP plus TQ versus DHA-PQP plus PQ and iii) DHA-PQP plus PQ versus DHA-PQP alone) of secondary efficacy endpoints (relapse-free efficacy at 4 months, time to relapse,

percentage of subjects with recrudescence, parasite clearance time, fever clearance time) will also be performed using survival analysis methodology.

A further sensitivity analysis will be performed in which all subjects will be categorized as either successes or failures at 6 months, analyzed using Exact methods. Subjects taking medication with anti-malarial efficacy during the study will be classified as failures in this analysis.

All safety endpoints will be based on the safety population and presented in tabular and/or graphical format and summarised descriptively according to GSK's Integrated Data Standards Library (IDSL) standards.

## **10 STUDY GOVERNANCE CONSIDERATIONS**

### **10.1 Posting of Information on Publicly Available Clinical Trial Registers**

Study information from this protocol will be posted on publicly available clinical trial registers before enrollment of subjects begins.

### **10.2 Regulatory and Ethical Considerations, Including the Informed Consent Process**

Prior to site initiation, GSK will obtain favourable opinion/approval from the appropriate regulatory agency to conduct the study in accordance with ICH Good Clinical Practice (GCP) and applicable country-specific regulatory requirements.

The study will be conducted in accordance with all applicable regulatory requirements, and with GSK policy.

The study will also be conducted in accordance with ICH Good Clinical Practice (GCP), all applicable subject privacy requirements, and the guiding principles of the current version of the Declaration of Helsinki. This includes, but is not limited to, the following:

- IRB/IEC review and favorable opinion/approval of the study protocol and amendments as applicable.
- Obtaining signed informed consent prior to participation in the study
- Investigator reporting requirements (e.g. reporting of AEs/SAEs/protocol deviations to IRB/IEC)
- GSK will provide full details of the above procedures, either verbally, in writing, or both.
- The IEC/IRB, and where applicable the regulatory authority, approve the clinical protocol.

### 10.3 Quality Control (Study Monitoring)

- In accordance with applicable regulations including GCP, and GSK procedures, GSK monitors (or designee) will contact the site prior to the start of the study to review with the site staff the protocol, study requirements, and their responsibilities to satisfy regulatory, ethical, and GSK requirements.
- When reviewing data collection procedures, the discussion will also include identification, agreement and documentation of data items for which the CRF will serve as the source document.

GSK (or their designee) will monitor the study and site activity to verify that the:

- Data are authentic, accurate, and complete.
- Safety and rights of subjects are being protected.
- Study is conducted in accordance with the currently approved protocol and any other study agreements, GCP, and all applicable regulatory requirements.

The investigator and the head of the medical institution (where applicable) agrees to allow the monitor direct access to all relevant documents.

### 10.4 Quality Assurance

- To ensure compliance with GCP and all applicable regulatory requirements, GSK or their representative may conduct a quality assurance assessment and/or audit of the site records, and the regulatory agencies may conduct a regulatory inspection at any time during or after completion of the study.
- In the event of an assessment, audit or inspection, the investigator (and institution) must agree to grant the advisor(s), auditor(s) and inspector(s) direct access to all relevant documents and to allocate their time and the time of their staff to discuss the conduct of the study, any findings/relevant issues and to implement any corrective and/or preventative actions to address any findings/issues identified.

### 10.5 Study and Site Closure

- Upon completion or premature discontinuation of the study, the GSK monitor will conduct site closure activities with the investigator or site staff, as appropriate, in accordance with applicable regulations including GCP, and GSK Standard Operating Procedures.
- GSK reserves the right to temporarily suspend or prematurely discontinue this study at any time for reasons including, but not limited to, safety or ethical issues or severe non-compliance. If GSK determines such action is needed, GSK will discuss the reasons for taking such action with the investigator or the head of the medical institution (where applicable). When feasible, GSK will provide advance notification to the investigator or the head of the medical institution, where applicable, of the impending action.
- If the study is suspended or prematurely discontinued for safety reasons, GSK will promptly inform all investigators, heads of the medical institutions (where

applicable) and/or institution(s) conducting the study. GSK will also promptly inform the relevant regulatory authorities of the suspension or premature discontinuation of the study and the reason(s) for the action.

- If required by applicable regulations, the investigator or the head of the medical institution (where applicable) must inform the IRB/IEC promptly and provide the reason for the suspension or premature discontinuation.

## **10.6 Records Retention**

- Following closure of the study, the investigator or the head of the medical institution (where applicable) must maintain all site study records (except for those required by local regulations to be maintained elsewhere), in a safe and secure location.
- The records must be maintained to allow easy and timely retrieval, when needed (e.g., for a GSK audit or regulatory inspection) and must be available for review in conjunction with assessment of the facility, supporting systems, and relevant site staff.
- Where permitted by local laws/regulations or institutional policy, some or all of these records can be maintained in a format other than hard copy (e.g., microfiche, scanned, electronic); however, caution needs to be exercised before such action is taken.
- The investigator must ensure that all reproductions are legible and are a true and accurate copy of the original and meet accessibility and retrieval standards, including re-generating a hard copy, if required. Furthermore, the investigator must ensure there is an acceptable back-up of these reproductions and that an acceptable quality control process exists for making these reproductions.
- The investigator must retain Investigator Site Files for 25 years from the final Clinical Study report date. The final retention date for Investigator Site Files will be provided at the same time as the Clinical Study report or equivalent results summary (local country law will apply where longer retention periods apply).
- The investigator must notify GSK of any changes in the archival arrangements, including, but not limited to, archival at an off-site facility or transfer of ownership of the records in the event the investigator is no longer associated with the site.

## **10.7 Provision of Study Results to Investigators, Posting of Information on Publicly Available Clinical Trials Registers and Publication**

Where required by applicable regulatory requirements, an investigator signatory will be identified for the approval of the clinical study report. The investigator will be provided reasonable access to statistical tables, figures, and relevant reports and will have the opportunity to review the complete study results at a GSK site or other mutually-agreeable location.

GSK will also provide the investigator with the full summary of the study results. The investigator is encouraged to share the summary results with the study subjects, as appropriate.

GSK will provide the investigator with the randomization codes for their site only after completion of the full statistical analysis.

The procedures and timing for public disclosure of the results summary and for development of a manuscript for publication will be in accordance with GSK Policy.

A manuscript will be progressed for publication in the scientific literature if the results provide important scientific or medical knowledge.

## **10.8 Review Committees**

Blinded safety data will be reviewed on a monthly basis by a GSK/MMV safety review board which includes a reviewer independent of the study sponsors.

## 12 APPENDICES

### 12.1 Appendix 1: Abbreviations and Trademarks

#### Abbreviations

ACT	Artemisinin-based combination therapy
AE	Adverse Event
ALP	Alkaline Phosphatase
ALT	Alanine Aminotransferase
AST	Aspartate Aminotransferase
AUC	Area Under the Curve
BUN	Blood Urea Nitrogen
CRA	Clinical Research Associate
CRF	Case Report Form
CPK	Creatine Phosphokinase
CQ	Chloroquine
CV	Cardiovascular
d	Day
DHA-PQP	Dihydroartemisinin Piperazine
DOT	Directly observed therapy
DRE	Disease-Related Event
DDI	Drug-drug Interaction
ECG	Electrocardiogram
eCRF	Electronic Case Report Form
FCT	Fever clearance time
FDA	Food and Drug Administration
FST	Fluorescent Spot Test
FU	Follow Up
HR	Heart rate
GI	Gastrointestinal
G6PD	Glucose-6-phosphate Dehydrogenase
GSK	GlaxoSmithKline
GCP	Good Clinical Practice
g	Grams
g/dL	Grams per Deciliter
Hb	Hemoglobin
Hct	Hematocrit
HIV	Human Immunodeficiency Virus
ICH	International Conference on Harmonization
IEC	Independent Ethics Committee
IRB	Institutional Review Board
INR	International Normalized Ratio
ITT	Intention to Treat
IWRS	Interactive web recognition test
kg	Kilograms

LDH	Lactate Dehydrogenase
m	Meter
MTA	Material Transfer Agreement
MSDS	Material Safety Data Sheet
MCV	Mean Cell Volume
MMV	Medicines for Malaria Venture
MetHb	Methemoglobin
µg.h/mL	Microgram Hours per milliliter
µL	Microliters
mg	Milligrams
mL	Milliliters
MTA	Material Transfer Agreement
PCR	Polymerase chain reaction
PCT	Parasite clearance time
PD	Pharmacodynamics
PGx	Pharmacogenetics
PK	Pharmacokinetics
PQ	Primaquine
RAP	Reporting and Analysis Plan
RBC	Red Blood Count
SAE	Serious Adverse Event
SRM	Study Reference Manual
TQ	Tafenoquine
ULN	Upper Limit of Normal
WBC	White Blood Count
WHO	World Health Organization

### Trademark Information

Trademarks of the GlaxoSmithKline group of companies
NONE

Trademarks not owned by the GlaxoSmithKline group of companies
EURARTESIM
NONMEM

## 12.2 Appendix 2: Liver Safety Required Actions and Follow up Assessments

**Phase III-IV liver chemistry stopping and increased monitoring criteria** have been designed to assure subject safety and evaluate liver event etiology (in alignment with the FDA premarketing clinical liver safety guidance).

<http://www.fda.gov/downloads/Drugs/GuidanceComplianceRegulatoryInformation/Guidances/UCM174090.pdf>

### Phase III-IV liver chemistry stopping criteria and required follow up assessments

Liver Chemistry Stopping Criteria - Liver Stopping Event	
ALT-absolute	ALT ≥ 8xULN
ALT Increase	ALT ≥ 5xULN but <8xULN persists for ≥2 weeks ALT ≥ 3xULN but <5xULN persists for ≥4 weeks
Bilirubin	ALT ≥ 3xULN and bilirubin ≥ 2xULN (>35% direct bilirubin)
INR^2	ALT ≥ 3xULN and INR>1.5, if INR measured
Cannot Monitor	ALT ≥ 5xULN but <8xULN and cannot be monitored weekly for ≥2 weeks ALT ≥ 3xULN but <5xULN and cannot be monitored weekly for ≥4 weeks
Symptomatic	ALT ≥ 3xULN associated with symptoms (new or worsening) believed to be related to liver injury or hypersensitivity
Required Actions and Follow up Assessments following ANY Liver Stopping Event	
Actions	Follow Up Assessments

 
Immediately discontinue study treatment
 
Report the event to GSK within 24 hours
 
Complete the liver event CRF and complete an SAE data collection tool if the event also meets the criteria for an SAE
 
Perform liver event follow up assessments
 
Monitor the subject until liver chemistries resolve, stabilize, or return to within baseline (see MONITORING below)
 
Do not restart/rechallenge subject with study treatment unless allowed per protocol and GSK Medical Governance approval is
 
	
 
Viral hepatitis serology
 
Only in those with underlying chronic hepatitis B at study entry (identified by positive hepatitis B surface antigen) quantitative hepatitis B DNA and hepatitis delta antibody.
 
Blood sample for pharmacokinetic (PK) analysis, obtained as soon as possible and within 24 hours of last dose, if liver event occurs within 60 days post-dose.
 
Serum creatine phosphokinase (CPK) and lactate dehydrogenase (LDH).
 


granted
 
 
If restart/rechallenge not allowed or not granted, permanently discontinue study treatment and may continue subject in the study for any protocol specified follow up assessments
 
 
MONITORING:
 
For bilirubin or INR criteria:
 
 
Repeat liver chemistries (include ALT, AST, alkaline phosphatase, bilirubin) and perform liver event follow up assessments within 24 hrs
 
Monitor subjects twice weekly until liver chemistries resolve, stabilize or return to within baseline
 
A specialist or hepatology consultation is recommended
 
 
For All other criteria:
 
 
Repeat liver chemistries (include ALT, AST, alkaline phosphatase, bilirubin) and perform liver event follow up assessments within 24-72 hrs
 
Monitor subjects weekly until liver chemistries resolve, stabilize or return to within baseline
 
	
 
Fractionate bilirubin, if total bilirubin <math>\geq 2 \times \text{ULN}</math>
 
Obtain complete blood count with differential to assess eosinophilia
 
Record the appearance or worsening of clinical symptoms of liver injury, or hypersensitivity, on the AE report form
 
Record use of concomitant medications on the concomitant medications report form including acetaminophen, herbal remedies, other over the counter medications.
 
Record alcohol use on the liver event alcohol intake case report form
 
 
For bilirubin or INR criteria:
 
 
Anti-nuclear antibody, anti-smooth muscle antibody, Type 1 anti-liver kidney microsomal antibodies, and quantitative total immunoglobulin G (IgG or gamma globulins).
 
Serum acetaminophen adduct HPLC assay (quantifies potential acetaminophen contribution to liver injury in subjects with definite or likely acetaminophen use in the preceding week [James, 2009]). NOTE: not required in China
 
Liver imaging (ultrasound, magnetic resonance, or computerised tomography) and /or liver biopsy to evaluate liver disease; complete Liver Imaging and/or Liver Biopsy CRF forms.
 

--	--

- Serum bilirubin fractionation should be performed if testing is available. If serum bilirubin fractionation is not immediately available, discontinue study treatment for that subject if ALT  $\geq 3 \times \text{ULN}$  and bilirubin  $\geq 2 \times \text{ULN}$ . Additionally, if serum bilirubin fractionation testing is unavailable, **record presence of detectable urinary bilirubin on dipstick**, indicating direct bilirubin elevations and suggesting liver injury.
- All events of ALT  $\geq 3 \times \text{ULN}$  and bilirubin  $\geq 2 \times \text{ULN}$  (>35% direct bilirubin) or ALT  $\geq 3 \times \text{ULN}$  and INR >1.5, if INR measured which may indicate severe liver injury (possible 'Hy's Law'), **must be reported as an SAE (excluding studies of hepatic impairment or cirrhosis)**; INR measurement is not required and the threshold value stated will not apply to subjects receiving anticoagulants
- New or worsening symptoms believed to be related to liver injury (such as fatigue, nausea, vomiting, right upper quadrant pain or tenderness, or jaundice) or believed to be related to hypersensitivity (such as fever, rash or eosinophilia)

4. Includes: Hepatitis A IgM antibody; Hepatitis B surface antigen and Hepatitis B Core Antibody (IgM); Hepatitis C RNA; Cytomegalovirus IgM antibody; Epstein-Barr viral capsid antigen IgM antibody (or if unavailable, obtain heterophile antibody or monospot testing); Hepatitis E IgM antibody
5. If hepatitis delta antibody assay cannot be performed, it can be replaced with a PCR of hepatitis D RNA virus (where needed) [Le Gal, 2005].
6. PK sample may not be required for subjects known to be receiving placebo or non-GSK comparator treatments. Record the date/time of the PK blood sample draw and the date/time of the last dose of study treatment prior to blood sample draw on the CRF. If the date or time of the last dose is unclear, provide the subject's best approximation. If the date/time of the last dose cannot be approximated OR a PK sample cannot be collected in the time period indicated above, do not obtain a PK sample. Instructions for sample handling and shipping are in the SRM.

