## 4.2. Treatment Arms and Duration

Subjects will receive open label DHA-PQP plus blinded tafenoquine or blinded primaquine or placebo as shown in the table below. Visually matching placebo medication will be used to maintain the blinding.

	Open label DHA-PQP	Blinded Tafenoquine or Placebo	Blinded Primaquine or Placebo
Arm 1 DHA-PQP alone (placebo arm)	Open label DHA-PQP tablets *  Single daily dose on Days 1-3	Placebo to match tafenoquine tablets 150mg (2 tablets)  Single dose on Day 1 or 2	Placebo to match overencapsulated primaquine tablets 15mg (1 capsule)  Single daily dose for 14 days commencing Day 1 or 2
Arm 2 DHA-PQP plus tafenoquine 300mg single dose	Open label DHA-PQP tablets*  Single daily dose on Days 1-3	Tafenoquine tablets 150mg (2 tablets)  Single dose on Day 1 or 2	Placebo to match overencapsulated primaquine tablets 15mg (1 capsule)  Single daily dose for 14 days commencing Day 1 or 2
Arm 3 DHA-PQP plus primaquine 15mg for 14 days	Open label DHA-PQP tablets*  Single daily dose on Days 1-3	Placebo to match tafenoquine tablets 150mg (2 tablets)  Single dose on Day 1 or 2	Overencapsulated primaquine tablets 15mg (1 capsule)  Single daily dose for 14 days commencing Day 1 or 2

\* Open label DHA-PQP (piperazine tetraphosphate (PQP) 320mg/ dihydroartemisinin (DHA) 40mg) tablets will be dosed according to weight (3 tablets per day for subjects weighing <75Kg and 4 tablets per day for subjects weighing ≥75Kg).

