**Phase III-IV Liver Chemistry Stopping and Increased Monitoring Algorithm**

As blinded tafenoquine study treatment is administered as a single dose, the above criteria for stopping medication do not apply. However, the liver safety required actions and follow up assessments must be followed if the stopping criteria are met – see [Appendix 2](#) (Section 12.2). The liver safety follow-up assessments will be carried out by a local commercial laboratory where possible. If assessments are not available in Indonesia, samples will be stored in Indonesia until such time as a Material Transfer Agreement (MTA), if necessary, is formally approved for the transfer of the sample to the designated laboratory for analysis.

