## 6. STUDY TREATMENT

‘Blinded study treatment’ refers to tafenoquine, primaquine and the corresponding placebos.

	Study Treatment				
Product name:	Tafenoquine (SB-252263)	Matched-Placebo for Tafenoquine	Primaquine	Matched-Placebo for Primaquine	DHA-PQP 320/40 dihydroartemisinin-piperaquine
Formulation description:	Each tablet will contain 150mg tafenoquine	Each tablet will contain tafenoquine matched-placebo	Each over-encapsulated tablet will contain 15mg primaquine	Each capsule will contain primaquine matched-placebo	Each tablet will contain 320mg piperaquine tetrasphosphate (as the tetrahydrate;PQP) and 40mg dihydroartemisinin (DHA)
Unit dose strength(s) /Dosage level(s):	150 mg tafenoquine	Placebo	Equivalent to 15mg primaquine base	Placebo	Equivalent to 40mg DHA and 320 PQP base
Route of Administration:	Administer orally	Administer orally	Administer orally	Administer orally	Administer orally
Dosing instructions:	Administer 2 tablets with water as a single dose after a meal. Dose to be taken at least 3 hours after DHA-PQP	Administer 2 tablets with water as a single dose after a meal. Dose to be taken at least 3 hours after DHA-PQP	Administer 1 capsule daily with water as a single dose after a meal for 14 days. Dose to be taken at least 3 hours after DHA-PQP (Days 1, 2 and 3).	Administer 1 capsule daily with water as a single dose after a meal for 14 days. Dose to be taken at least 3 hours after DHA-PQP (Days 1, 2 and 3).	Single dose for 3 days  3 tablets per day for subjects <75Kg  4 tablets per day for subjects ≥75Kg  Dose to be taken at least 3 hours after last food intake. No food to be taken for at least 3 hours after dosing

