**7.1. Time and Events Table**

Procedures	Visit Day (Treatment Period Days 1-14)															
	1	1		2 b	3	4	5	6	7	8	9	10	11	12	13	14
	Pre DHA-PQP	DHA-PQP	Blinded med a													
Written Informed Consent	x															
Subject Demography	x															
Medical History	x															
Disease History	x															
Signs & Symptoms	x	x														
Therapy History	x															
Inclusion/Exclusion Criteria	x															
Efficacy Assessments																
Blood smears	x			x c	x c				x							x
Plasmodium PCR genotyping/sequencing	x															
Safety Assessments																
Concomitant Medication	x	x		x	x	x	x	x	x	x	x	x	x	x	x	x
Physical Examination	x			x	x				x							
Vital Signs d	x			x	x o				x							x
12-lead ECG e	x				x				x							
Adverse Events f			x	x	x	x	x	x	x	x	x	x	x	x	x	x
Serious Adverse Events g	x	x		x	x	x	x	x	x	x	x	x	x	x	x	x
G6PD (phenotyping) h	x															
G6PD/CYP2D6 (genotyping) i	x															
Laboratory Assessments																
Hematology/Clin.Chem/urinalysis j	x				x		x		x							x
Methemoglobin l	x			x	x	x	x	x	x	x	x	x	x	x	x	x
PK sampling	x		x k						x							x
Investigational Product																
Dispense Open Label DHA-PQP		x		x	x											
Dispense Blinded Study Treatment (access IWRS on day 1 only)			x	x	x	x	x	x	x	x	x	x	x	x	x	x

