## Time and Events Table (Continued)

Procedures	Visit Day (Follow Up Period)									
	21	28	60	90	120	150	180	195 p (only for subjects who have not relapsed prior to Day 180)	Relapse	Withdrawal from study
Window	-/+3d	-3d, +15d	-16 d, +15d	-14d, +15d	-14d, +15d	-14d, +19d	-/+10d	Day 180 + 15d to 21d		
Efficacy Assessments										
Parasitological Assessment (blood smears)	x	x	x	x	x	x	x		x	x
Plasmodium PCR genotyping/sequencing									x	
Safety Assessments										
Concomitant Medication	x	x	x	x	x	x	x	x	x	x
Physical Examination	x	x	x	x	x	x	x		x	x
Vital Signs d	x	x	x	x	x	x	x		x	x
12-lead ECG e		x							x	x
Adverse Events	x	x	x	x	x	x	x	x	x	x
Serious Adverse Events	x	x	x	x	x	x	x	x	x	x
Dispense rescue treatment (ACT+PQ)									x	
Laboratory Assessments										
Hematology/Clinical Chemistry	x	x	x	x	x				x m	x m
Methemoglobin l	x	x	x						x	x
PK Sampling		x	x						x n	
Open Label Primaquine										
Dispense open label PQ –only for subjects who have not relapsed prior to D180							x			

Time and Event Table Notes:

- a) Blinded study treatment may be started on Day 1 or Day 2. If started on Day 2, blinded primaquine/placebo is given from Day 2-15.
- b) If a subject starts blinded study treatment on Day 2, the following assessments should be completed on Day 15: Concomitant medication, AEs/SAEs, methemoglobin, dispense blinded study treatment.
- c) Blood smears to be taken twice daily until two consecutive negative smears 6-12 hours apart.
- d) Vital signs include height and weight (screening only), blood pressure, temperature, heart rate and respiratory rate.
- e) ECGs will be done in triplicate on Day 1 (prior to DHA-PQP). Subsequent ECGs will be done as single ECGs unless prolonged QTcF is seen. ECG timings post baseline will be as follows: 1) Before the last of the three daily doses of DHA-PQP 2) 4 hours (window -1 to +2 hours) after last dose of DHA-PQP, 3) Day 7, 4) Day 28 and 5) relapse/withdrawal if within 28 days post-dose.
- f) Adverse events are recorded from the time of the first dose of study treatment.
- g) Serious adverse events are recorded from the time of consent in order to fulfil international regulatory requirements.
- h) G6PD phenotyping to be performed by suitable qualitative test (refer to SRM) and quantitative spectrophotometric analysis.

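### The liver-event PK sample is requested for events up to 60 days post-dose but must be drawn within 24 hours of the last dose, so from about Day 16 it cannot be taken as written

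*Protocol*

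**What the plan says.** Protocol Appendix 2 (Section 12.2) lists, among the follow-up assessments after any liver stopping event, a PK blood sample "obtained as soon as possible and within 24 hours of last dose, if liver event occurs within 60 days post-dose". Footnote 6 adds that if "a PK sample cannot be collected in the time period indicated above, do not obtain a PK sample". The same footnote asks the site to record "the date/time of the last dose of study treatment prior to blood sample draw", which ties the timing to study treatment and not to tafenoquine alone.

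Section 6 says that blinded study treatment "refers to tafenoquine, primaquine and the corresponding placebos". In Section 4.2 the primaquine or matching placebo capsule is given in all three arms as "Single daily dose for 14 days commencing Day 1 or 2"; tafenoquine or its placebo is given once, on Day 1 or 2. Section 5.4.1 states: "As blinded tafenoquine study treatment is administered as a single dose, the above criteria for stopping medication do not apply". It then says that the liver safety actions and follow-up assessments must still be carried out. Appendix 2, for its part, tells sites to discontinue study treatment at once after a liver stopping event.

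**The concern.** The bullet contains two time limits. One says which events call for a sample (those up to 60 days post-dose); the other says when the sample may be drawn (within 24 hours of the last dose). Once dosing has ended, no event can satisfy both, and footnote 6 turns a missed window into an instruction not to sample.

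The protocol otherwise treats later tafenoquine concentrations as worth having. Section 5.4 cites the long half-life and warns that effects may peak days after dosing. Routine PK sampling runs to Day 60. At relapse, note n to the Time and Events Table asks for PK as close to the event as possible up to Day 60, with no 24-hour condition.

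At stake is a plasma concentration near a liver event, which would help to judge whether the event is related to exposure. A site that follows the text as written would not draw it for events that appear after the capsules finish.

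**Working it through.** The plan gives no figure to reproduce. The check is a day count.

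**Inputs**
- Sample window 24 hours after the last dose; event period 60 days post-dose (Appendix 2).
- First blinded dose on Day 1 or 2; 14 daily capsules, so the last capsule falls on Day 14 or 15 (Section 4.2; Section 7.1, note a). Open-label DHA-PQP ends on Day 3 and does not extend the window.
- Scheduled post-dose chemistry to Day 60: Days 3, 5, 7 and 14 (row "Hematology/Clin.Chem/urinalysis"), then Days 21, 28 and 60 (row "Hematology/Clinical Chemistry").
- Routine PK from Day 7 to Day 60: Days 7, 14, 28 and 60 (Sections 4.1 and 7.1).

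**Reading A: the last dose is any blinded study treatment (footnote 6)**
- Days on which a draw can comply = (last capsule day + 1) − start day. Day 1 start: (14 + 1) − 1 = 14. Day 2 start: (15 + 1) − 2 = 14.
- Share of the 60 days: 14/60 = 23%. The remaining 46/60 = 77% cannot be served. Counted as calendar days, Day 16 to Day 60 is 60 − 16 + 1 = 45 days.
- If the 60 days run from the last capsule, the period is 13 + 60 = 73 days and the share is 14/73 = 19%.

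**Reading B: the last dose is tafenoquine**
- 1/60 = 1.7% of days qualify.

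| Scheduled chemistry | Reading A | Reading B | Routine PK at same visit |
|---|---|---|---|
| Day 3 | inside | inside only if dosed Day 2 | no |
| Day 5 | inside | outside | no |
| Day 7 | inside | outside | yes |
| Day 14 | inside | outside | yes |
| Day 21 | outside | outside | no |
| Day 28 | outside | outside | yes |
| Day 60 | outside | outside | yes |

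Under Reading A, 4 of the 7 visits are inside the window and 3 are outside.

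**Persistence-based ALT criteria.** Entry excludes ALT above 2×ULN (Section 5.2), and the first scheduled on-study chemistry is Day 3. The earliest dates, counting from a scheduled draw, are:
- ALT at least 5×ULN (below 8×ULN) for 2 weeks or more: Day 3 + 14 = Day 17.
- ALT at least 3×ULN (below 5×ULN) for 4 weeks or more: Day 3 + 28 = Day 31.

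Both fall after Day 16. An unscheduled finding on Day 2 would give Day 2 + 14 = Day 16, at the edge of the window for a Day 2 start.

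**Events during dosing.** For criteria other than bilirubin or INR, Appendix 2 allows 24 to 72 hours for the follow-up assessments. If capsules stop at the event, an assessment late in that range is already more than 24 hours from the last dose.

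**The case against.** Three stronger conclusions are tempting, and the documents do not support them.

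- A reader might infer that the sample can almost never be taken. That holds only if the last dose means the tafenoquine dose. Footnote 6 refers to study treatment, every arm takes a daily capsule, and 4 of the 7 chemistry visits to Day 60 are inside the window.
- A reader might infer that exposure data for a liver signal are lost. Tafenoquine PK is drawn regardless of liver events, and two of the three barred visits (Days 28 and 60) have a routine PK sample. SAP Section 9 plans individual post hoc PK parameters if the existing model predicts adequately. Protocol Section 7.6.1 lets the sponsor add PK samples. The sponsor must hear within 24 hours of a liver stopping event, and also of the earlier ALT rise that starts increased monitoring, so it could often request a draw in time.
- A reader might infer that the persistence criteria can never qualify. The Day 17 and Day 31 figures assume that the rise is first seen at a scheduled draw, so almost always is the most that can be said.

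The time period in footnote 6 could also be read as the 60 days. In the bullet, however, the 60 days qualify the event and the 24 hours qualify the sample. Even on the kinder reading, the 24-hour limit in the bullet remains.

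The consequence is also small. No liver display in the SAP uses this sample, and PK is reported separately and later.

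These points limit the size of the problem but do not remove the conflict. A discretionary provision does not cancel an explicit instruction to the site. Days 28 and 60 are 32 days apart, Day 21 has no routine PK, and the withdrawal visit has none, so an event at those times may have no concurrent concentration.

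**Conclusion.** The conflict is real and its effect is limited. With the capsule counted as the last dose, the sample is barred for about 45 of the 60 days, including the Day 21, 28 and 60 chemistry visits, and for almost every event that meets a persistence-based ALT criterion. Events found on Days 3, 5, 7 or 14 can usually be sampled. With tafenoquine as the last dose, about 1 day in 60 qualifies.

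These figures assume that all 14 capsules are taken on schedule, that the 60 days run from the first blinded dose, and that footnote 6 has its plain meaning. Stopping capsules early would close the window sooner.

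The loss is the concentration near the event in the participants who have one. Routine, discretionary and model-based exposure information remains. The primary analysis and power are unaffected.

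**What to change.** Amend the protocol, since both clauses are protocol text:

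1. Reconcile the Appendix 2 PK bullet, its 24 to 72 hour timing for follow-up assessments, footnote 6 and Section 5.4.1. Section 5.4.1 and Appendix 2 also differ on whether the criteria for stopping medication apply. That must be settled by those responsible for clinical management; this point takes no position on it.
2. State which dose the 60 days and any other time limit refer to.
3. Replace the 24-hour limit, and the matching condition in footnote 6, with one PK sample as soon as possible after the liver event is identified, for events within the 60-day period already stated. Record the dates and times of the tafenoquine or placebo dose and of the last capsule.

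The cost is a minor amendment and one tube at a follow-up visit already required, in the few participants with an event. The population PK dataset in SAP Appendix 9 already carries sample date, time and time since the tafenoquine dose, so it can hold a sample taken at any time. No dose or treatment rule changes.

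SAP Section 2.1 records that 150 participants had been randomised when the SAP was finalised. For anyone past the 60-day period an amendment comes too late; the PK report can then state, for each liver event, how close the nearest concentration was.
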